11 SAFETY ANALYSIS

Unless otherwise indicated, safety data will be summarized overall and by treatment group and visit, when applicable, for each study period separately, based on the SAF for the DB Treatment Period and OLE SAF for the OLE Period.

11.1 Adverse Events

AEs will be coded according to the MedDRA, Version 24.1, and will be summarized overall and by treatment group for across both study periods and for each study period separately.

Treatment emergent adverse events (TEAEs) are defined as any AEs with onset date during or after the first study treatment dose. See Appendix 2 for handling of completely or partially missing dates for AEs. AEs starting on the first study treatment dosing date and related to a pre-dose study assessment will not be considered as TEAE. In the case where it is not possible to define an AE as treatment emergent or not, the AE will be classified as treatment emergent.

Furthermore, TEAEs will be assigned to the DB Treatment Period or OLE Period depending on their onset date – if the AE onset date is before the date of first dose in OLE, the AE will be assigned to the DB Treatment Period AE. If the AE had an onset on or after the date of first dose in OLE, the AE will be assigned to an OLE Period. AEs starting on the Week 24 and related to a pre-dose study assessment will be assigned to DB Treatment Period.

An overall summary table of adverse events will be provided. The number of events and the frequency count and percentage of subjects who experienced an AE, TEAE, TEAE by maximum reported relationship, TEAE by maximum reported Common Terminology Criteria for Adverse Events (CTCAE) severity, serious AE (SAE), serious TEAE, TEAE leading to study drug

discontinuation, TEAE leading to study discontinuation, treatment emergent AE of Special Interest (AESI) and AE leading to death will be presented.

Of note, prior to each database lock (primary and final), AESIs will be flagged as such by the Sponsor Clinical Development/Medical teams from the subset of AEs that will have been classified programmatically as Targeted Medical Events (TMEs) based on an exhaustive list of SOCs and PTs provided by the Sponsor. The list of AEs deemed as AESIs will be finalized prior to each database lock.

Unless otherwise specified, a subject experiencing a TEAE multiple times within the same PT will be counted only once for the corresponding PT. Similarly, if a subject experiencing multiple TEAEs within the same SOC, the subject will be counted only once for that SOC. TEAEs will be sorted by decreasing order of total frequency of SOC and PT within each SOC.

Frequency and percentage of subjects who experience TEAE will be summarized by PT and also by SOC and PT.

Frequency and percentage of subjects who experience TEAE will be summarized by SOC, PT, and maximum reported relationship (treatment-related or not treatment-related). A treatment-related AE is defined as any TEAE that is assessed by the Investigator as Related or Probably Related to study treatment. TEAE that is assessed as Unlikely Related or Not Related will be defined as not treatment-related. TEAE with an unknown relationship will be considered as treatment-related.

Frequency and percentage of subjects who experience TEAE will be summarized by SOC, PT, and maximum reported severity. The severity will be graded according to the CTCAE (Grade 1 - mild, Grade 2 - moderate, Grade 3 - severe, Grade 4 – life-threatening or Grade 5 - death). If a subject experience more than one TEAE within different severity categories within the same SOC/PT, only the worst case (maximum reported severity) will be reported. TEAE with an unknown severity will be considered as severe.

Frequency and percentage of subjects who experience serious TEAE will be summarized by SOC and PT within SOC.

Frequency and percentage of subjects who experience treatment emergent AESI will be summarized by AESI category and PT.

Frequency and percentage of subjects who experience non-serious TEAE will be summarized by SOC and PT for DB and OLE period separately.

Listings of all AEs, all AEs leading to death, all serious AEs, all TEAEs leading to study drug discontinuation, and all TEAEs leading to study discontinuation will be provided.

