10.5.7.5. Holter Monitoring

Continuous Holter recording will be performed for subjects from 15 minutes pre-treatment through 8 hours post-treatment any time a subject transitions from 2 mg to 3 mg etrasimod and at all timepoints specified in [Appendix 1](#) and [Appendix 2](#). A subject will be discharged from the study site with the Holter monitor in place and continue to wear the Holter monitor until Hour 8 (\pm 15 minutes) post-treatment administration. Subjects will be instructed how to remove and store the Holter monitor, record the time the device is removed, and to return the device for analysis at the next in-person study visit. If the subject requires extended in-clinic cardiac monitoring \geq 8 hours, the Holter will be removed on-site at Hour 8 prior to discharge. Holter data will be captured on the device and sent to the Holter laboratory. The Holter laboratory will be responsible for central reading, analysis, and interpretation. Holter recording results may be made available to study sites.

Holter recording will principally be used for determination of HR and potential arrhythmias (eg, pauses, AV block). Point estimates will be obtained at specified times. The central Holter laboratory may determine additional parameters or perform additional analyses from digitized Holter monitor recordings including but not limited to those indicated by the initial analyses or safety events. Additional information is provided in the Holter manual.

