10.5.8.2. Eliciting, Recording, and Reporting Adverse Events

10.5.8.2.1. Eliciting Adverse Events

Subjects will be instructed that they may report AEs at any time. An open-ended or nondirected method of questioning should be used at each study visit to elicit the reporting of AEs.

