11.2. Determination of Sample Size

Subjects will be randomized as follows:

- Cohort 1: 36 subjects in 2:1 randomization ratio (24 subjects to etrasimod 2 mg and 12 subjects to placebo)
- Cohort 2: 42 subjects with SALT I < 95 at Baseline in 4:1:2 randomization ratio (24 subjects to etrasimod 3 mg, 6 subjects to etrasimod 2 mg, and 12 subjects to placebo)

Assuming a 15% drop-out rate from the study over 24 weeks, at least 35 treatment completers (20 subjects to etrasimod 3 mg, 5 subjects to etrasimod 2 mg, and 10 subjects to placebo from Cohort 2; plus subjects from Cohort 1 with SALT I < 95 at Baseline) at Week 24 will provide at least 80% and 47% power to detect a treatment difference of 20% for etrasimod 3 mg and etrasimod 2 mg from placebo, respectively, in the percent change from Baseline in SALT I at Week 24 by a 2-sample t-test using a 2-sided significance test level of 0.05 and common standard deviation (SD) of 17.8%.

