2.2.1.4 Safety Endpoints

- Incidence and severity of adverse events (AEs) throughout the DB Treatment Period
- Incidence and severity of laboratory abnormalities and change from Baseline in laboratory values (to include hematology, serum chemistry, coagulation, and urinalysis) at Weeks 1 (Cohort 2 only), 2, 4, 8, 12, 16, 20, and 24
- Incidence of clinically significant vital sign abnormalities and changes from Baseline at 1-, 2-, 3-, and 4-hour post-dose on Day 1 as well as Weeks 1 (Cohort 2 only), 2, 4, 8, 12, 16, 20, and 24
- Electrocardiograms (ECG) at 4-hour post-dose on Day 1 as well as Weeks 12 and 24
- Holter Monitoring on Day 1 (Cohort 2 only) and Week 1 (Cohort 2 only)*
- Physical examination findings (abnormalities will be recorded and summarized as medical history or AEs, as applicable)

* The statistical analysis to be performed for these endpoints will be described in a separated SAP (refer to Section 1)

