3.4 Schedule of Events

For the statistical analysis, DB Treatment Period will include 24 weeks treatment; OLE Period will include 28 weeks treatment and 4 weeks SFU. The date at which the subject is randomized will be referred to as the “Day 1/Baseline”. Subjects will be requested to attend the following scheduled visits for the DB Treatment Period from their Day 1/Baseline visit: Weeks 1, 2, 4, 8, 12, 16, 20, 24 visits as applicable (Week 1 visit is applicable to Cohort 2 only). For the OLE Period, subjects will attend scheduled visits at Week 24 (this will be same as Week 24 in the DB Treatment Period), and Weeks 25, 28, 36, 44, and 52. Subjects who terminate the study drug early in the DB Treatment Period or OLE Period should have SFU Visits 2 weeks and 4 weeks after the last dose of study drug. Visits subjects make to the clinic outside the visit window are recorded as unscheduled visits. Refer to Schedules of Assessments (Appendix 1 and Appendix 2 in the protocol) for more details.

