5.7 Examination of Subgroups

Subgroup analysis by below variables will be performed using descriptive statistics only based on the following analysis set for the primary and secondary efficacy endpoints of the DB Treatment Period (refer to Sections 10.1 and 10.2, respectively) to explore whether the treatment effects are

consistent across different subgroups. Median will be derived based on subjects specific to each analysis set.

- Sex (male, female) – FAS
- Race (white, non-white) – FAS
- Age (\leq or $>$ median) – FAS
- Baseline SALT I score (\leq or $>$ median) – FAS
- Duration of AA from initial onset (\leq or $>$ median) – FAS
- Current disease duration (0 - $<$ 2.5 years, 2.5 years - $<$ 5 years, \geq 5 years): from onset of current episode – FAS
- Baseline AASIS (\leq or $>$ median) – FAS
- Baseline AA-QLI (\leq or $>$ median) – FAS

Additionally, subgroup analysis by below variables will also be performed using descriptive statistics only based on the following analysis set for demographic and other baseline characteristics (refer to Section 6.1), disposition of subjects (refer to Section 7.1), primary and secondary efficacy endpoints of the DB Treatment Period (refer to Sections 10.1 and 10.2, respectively), and exploratory efficacy endpoint of percent change from baseline in peripheral lymphocyte counts of the DB Treatment Period (refer to Section 10.3).

- Cohort (1 or 2) – FAS
- Baseline SALT I score ($<$ 50 or \geq 50) – FAS
- Baseline SALT I score ($<$ 50, \geq 50 to $<$ 95 or \geq 95) – Randomized Set
- Current disease duration ($<$ 5 years, \geq 5 years): from onset of current episode – FAS

The overall summary of AEs during the DB Treatment Period (refer to Section 11.1) and summary of vital signs of the observed and change from pre-dose values at Day 1 and Week 24 (refer to Section 11.3) will also be summarized by these subgroups for SAF.

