Table 14.2.2.3.9	Subgroup Analysis: Summary of Proportion of Subjects Achieving Improvement in SALT I - Non-Responder Imputation - Double-Blind Treatment Period - Current Disease Duration (Full Analysis Set)
Table 14.2.5.1.1	Summary and Statistical Analysis of Percent Change from Baseline in Peripheral Lymphocyte Counts - Observed Cases - Double-Blind Treatment Period (Full Analysis Set)

Table Number	Table Title
Table 14.2.5.1.2.1	Subgroup Analysis: Summary of Percent Change from Baseline in Peripheral Lymphocyte Counts - Observed Cases - Double-Blind Treatment Period - Cohort (Full Analysis Set)
Table 14.2.5.1.2.2	Subgroup Analysis: Summary of Percent Change from Baseline in Peripheral Lymphocyte Counts - Observed Cases - Double-Blind Treatment Period - Baseline SALT I Score (< 50, >= 50) (Full Analysis Set)
Table 14.2.5.1.2.3	Subgroup Analysis: Summary of Percent Change from Baseline in Peripheral Lymphocyte Counts - Observed Cases - Double-Blind Treatment Period - Baseline SALT I Score (< 50, >=50 to < 95, or >=95) (Randomized Set)
Table 14.2.5.1.2.4	Subgroup Analysis: Summary Analysis of Percent Change from Baseline in Peripheral Lymphocyte Counts - Observed Cases - Double-Blind Treatment Period - Current Disease Duration (Full Analysis Set)
Table 14.2.7	Summary and Statistical Analysis of Proportion of Subjects Achieving a SALT I Score ≤ 10 and ≤ 20 – Observed Cases - Double-Blind Treatment Period (Full Analysis Set)
Table 14.2.8	Summary of Change and Percent Change from Baseline in SALT I Score at Week 36 - Observed Cases - Open-Label Extension Period (Open-Label Extension Full Analysis Set)
Table 14.2.9	Summary of Proportion of Subjects Achieving Improvement in SALT I at Week 36 - Observed Cases - Open-Label Extension Period (Open-Label Extension Full Analysis Set)
Table 14.2.13	Summary of Proportion of Subjects Achieving a SALT I Score ≤ 10 and ≤ 20 at Week 36 – Observed Cases - Open-Label Extension Period (Open-Label Extension Full Analysis Set)
Table 14.3.1.1.1	Overall Summary of Adverse Events - Double-Blind Treatment Period (Safety Set)
Table 14.3.1.2.1	Summary of Treatment Emergent Adverse Events by System Organ Class and Preferred Term - Double-Blind Treatment Period (Safety Set)
Table 14.3.1.5.1	Summary of Treatment Emergent Adverse Events by System Organ Class, Preferred Term and Maximum Reported CTCAE Severity - Double-Blind Treatment Period (Safety Set)

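### Double-blind adverse events pool two cohorts with different detection schedules, leaving the arm comparisons open to distortion, and the by-cohort overview promised in SAP 5.7 is missing from the output list

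*SAP*

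**What the plan says.** **Presentation.** SAP 11.1 states that AEs "will be summarized overall and by treatment group for across both study periods and for each study period separately". The groups are the three arms with both cohorts combined, and the section contains no cohort split.

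**Detection schedule.** The double-blind safety endpoints in SAP 2.2.1.4 include "Holter Monitoring on Day 1 (Cohort 2 only) and Week 1 (Cohort 2 only", and SAP 3.4 notes that the "Week 1 visit is applicable to Cohort 2 only". Protocol Appendix 2 gives that visit a complete physical examination, laboratory tests, vital signs and an AE assessment. Appendix 1, for Cohort 1, has no Week 1 column and schedules Holter only at Weeks 24 and 25. On elicitation, Protocol 10.5.8.2.1 says: "An open-ended or nondirected method of questioning should be used at each study visit to elicit the reporting of AEs". Holter recordings are read centrally, and under Protocol 10.5.7.5 "Holter recording results may be made available to study sites".

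**Allocation.** Protocol 11.2 gives Cohort 1 as "36 subjects in 2:1 randomization ratio (24 subjects to etrasimod 2 mg and 12 subjects to placebo". Cohort 2 is 42 subjects at 4:1:2, that is 24 on 3 mg, 6 on 2 mg and 12 on placebo.

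**Cohort split.** SAP 5.7 lists cohort among its subgroups and commits to "The overall summary of AEs during the DB Treatment Period (refer to Section 11.1" being repeated by subgroup on the Safety Set, together with the Day 1 and Week 24 vital signs. For the double-blind overview, Appendix 3 lists only Table 14.3.1.1.1, "Overall Summary of Adverse Events - Double-Blind Treatment Period (Safety Set". The same list has separately numbered by-cohort tables for disposition, demographics, SALT I and lymphocyte counts.

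**The concern.** The arms are spread unevenly over two cohorts that are not looked at equally often. Every 3 mg subject is on the schedule with more detection opportunities, against half of the placebo group and a fifth of the 2 mg group. Part of any difference between arms in a pooled table can therefore reflect who was monitored.

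Safety is part of the primary objective. Protocol 1.2 describes the atrioventricular block seen so far as rare, asymptomatic and transient, which is the kind of finding whose recorded frequency depends on monitoring. The Week 1 Holter also coincides with the step from 2 mg to 3 mg in the 3 mg arm. Such terms would appear in the SOC/PT and AESI tables, and these are not planned by cohort. For SALT I, by contrast, SAP 10.1 plans a cohort-adjusted and a Cohort 2-only sensitivity analysis.

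**Working it through.** **1. Planned arm sizes (Protocol 11.2, SAP 3.2).** Cohort 1: 36 × 2/3 = 24 and 36 × 1/3 = 12. Cohort 2: 42 × 4/7 = 24, 42 × 1/7 = 6 and 42 × 2/7 = 12. These match the plan. The documents state no AE rate and no detection figure.

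**2. Share of each pooled arm on the Cohort 2 schedule.**

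| Arm | Cohort 1 | Cohort 2 | Share in Cohort 2 |
|---|---|---|---|
| 3 mg | 0 | 24 | 24/24 = 1.0 |
| Placebo | 12 | 12 | 12/24 = 0.5 |
| 2 mg | 24 | 6 | 6/30 = 0.2 |

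After Day 1 there are 7 scheduled double-blind visits in Cohort 1 and 8 in Cohort 2. The mean per pooled arm is 8.0 on 3 mg, 7.5 on placebo and 7.2 on 2 mg.

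**3. Effect of pooling.** Let b be the probability that an event is recorded under the Cohort 1 schedule, and e the extra probability under the Cohort 2 schedule. With no drug effect, the recorded rate in an arm is b + e × share. The background b cancels in differences:

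- 3 mg minus placebo: (1.0 - 0.5)e = +0.5e
- 2 mg minus placebo: (0.2 - 0.5)e = -0.3e
- 3 mg minus 2 mg: (1.0 - 0.2)e = +0.8e

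| Assumed e (points) | 3 mg - placebo | 2 mg - placebo | 3 mg - 2 mg |
|---|---|---|---|
| 5 | +2.5 | -1.5 | +4 |
| 10 | +5 | -3 | +8 |
| 20 | +10 | -6 | +16 |

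**4. Within cohort.** Both arms of a comparison have the same schedule, so the schedule-driven difference is zero by design.

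**5. Precision cost for 3 mg versus placebo.** Take an assumed b of 20% and e of 10 points. The rate is 0.30 under the Cohort 2 schedule and 0.25 in pooled placebo.

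- Pooled, 24 vs 24: SE = √(0.30 × 0.70/24 + 0.25 × 0.75/24) = 0.129
- Cohort 2, 24 vs 12: SE = √(0.30 × 0.70/24 + 0.30 × 0.70/12) = 0.162

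With an assumed b of 5% and the same e, the SE goes from 0.095 to 0.126.

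**The case against.** **The size is unknown and may be small.** Protocol 1.2 puts the heart-rate effect at its maximum on the first day, about 3 hours after the dose. Both cohorts have hourly vital signs for 4 hours and a 4-hour ECG on Day 1. A symptom at Week 1 in Cohort 1 can still be reported at Week 2. Sites are blinded to white-cell and lymphocyte results, so the extra laboratory draw adds less than it seems. Holter results reach sites only at discretion, and SAP 2.2.1.4 places their analysis in a separate SAP. All of this stands. It narrows the concern to asymptomatic rhythm or conduction findings and events picked up at Week 1, and it leaves the direction unchanged.

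**A reader might infer a spurious doubling against placebo and a fivefold excess over 2 mg.** Those ratios (1.0/0.5 and 1.0/0.2) need an event that the Cohort 1 schedule never detects and that is always recorded as an AE in Cohort 2. The documents do not support that. With an assumed b of 10% and e of 5 points, the ratios are 0.15/0.125 = 1.2 and 0.15/0.11 = 1.36.

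**A reader might also infer that serious events are affected, or that the SAP plans no AE data by cohort.** Serious AEs are reportable within 24 hours of awareness whatever the visit schedule (Protocol 10.5.8.3.1), so a material effect is unlikely. The overview promised in SAP 5.7 already carries serious-event and AESI counts.

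**The output-list gap may be clerical.** The by-subgroup vital-sign tables promised in the same sentence are also unlisted, and layouts are held in a separate document (SAP 4). That is plausible, but it would not supply the SOC/PT tables.

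**Cohort 2 tables are thin.** One event is 8.3% of 12 placebo subjects and 16.7% of 6 on 2 mg. This is a good reason to keep the pooled tables and to limit the within-Cohort 2 reading to events that the schedule can plausibly affect.

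**Conclusion.** The pooled double-blind AE comparisons are open to distortion. The direction is known: 3 mg looks worse than placebo, 2 mg looks better than placebo, and the step from 2 mg to 3 mg looks steeper. The size is +0.5e, -0.3e and +0.8e. It rests on the planned allocation, an extra detection probability e equal in all arms, and no drug effect on the event concerned. Because e is not in the documents, the figures for 5 to 20 points are illustrations, and they do not show that the tables will be materially wrong. The AE tables are descriptive, so the harm is to interpretation and no test is invalidated.

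Two gaps stand whatever the size of e: the by-cohort overview in SAP 5.7 has no entry in Appendix 3, and TEAEs by SOC/PT and AESIs by preferred term are not planned by cohort. Both are worth closing before the primary database lock.

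**What to change.** 1. Add the by-cohort double-blind AE overview to SAP Appendix 3, as SAP 5.7 already commits to it.
2. Add by-cohort double-blind tables of TEAEs by SOC/PT and of AESIs by preferred term, beside the pooled ones.
3. State in SAP 11.1 that, for cardiac rhythm or conduction events and events detected at Week 1, 3 mg versus placebo is read within Cohort 2, where the arms were randomised together and monitored alike. Fix the terms covered before the primary database lock.
4. Footnote the schedule difference on the pooled tables.

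Cohort-stratified risk differences are optional. For 2 mg versus placebo, the Mantel-Haenszel weights from planned numbers would be 24 × 12/36 = 8 for Cohort 1 and 6 × 12/18 = 4 for Cohort 2. For 3 mg the estimate reduces to the Cohort 2 comparison.

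The cost is some SAP wording, a few more tables, and a placebo denominator of 12 for the affected events, with the loss of precision shown in the working. Trial conduct does not change.

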10.5.8.1.5. Severity

The severity of each AE will be assessed at the onset by the Investigator. When recording the outcome of the AE, the maximum severity of the AE experienced will also be recorded. The severity of each AE will be graded according to the CTCAE:

- | | |
|----------|---|
| Grade 1: | Mild; asymptomatic or mild symptoms; clinical or diagnostic observations only; intervention not indicated. |
| Grade 2: | Moderate; minimal, local or noninvasive intervention indicated; limiting age-appropriate instrumental activities of daily living. |
| Grade 3: | Severe or medically significant but not immediately life-threatening; hospitalization or prolongation of hospitalization indicated; disabling, limiting self-care activities of daily life (eg, preparing meals, shopping for groceries or clothes, using the telephone, managing money). |
| Grade 4: | Life-threatening consequences, urgent intervention indicated. |
| Grade 5: | Death related to AE. |

Additional information on CTCAE grading of AEs is provided in [Appendix 4](#).

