10.5.8.2.2. Recording Adverse Events

The AE reporting period for safety surveillance begins when the subject is initially included in the study (date of first signature of informed consent) and continues up to 30 days after the last study drug administration. If an AE is not resolved or stabilized by this time, the Sponsor in consultation with the Investigator will decide whether to continue to monitor the AE or closeout the event in the database if no further follow-up is necessary.

Any SAE suspected to be related to the study drug must be reported whenever it occurs, irrespective of the time elapsed since the last administration.

Investigator and study personnel will record all AEs and SAEs whether received through an unsolicited report by a subject, elicited during subject questioning, discovered during physical examination, laboratory testing, and/or other means by recording them on the eCRF and SAE Report Form, as appropriate. The following information should be recorded on the AE eCRF:

- Description including onset and resolution dates
- Whether it met SAE criteria
- Severity
- Relationship to study drug or other causality
- Action taken with study drug

- Outcome

For SAEs, events occurring secondary to the primary event should be described on the SAE Report Form in the narrative description field.

The following should be considered when recording SAEs:

- Death is an outcome of an event. The event that resulted in the death should be recorded and reported on the SAE Report Form and eCRF.
- For hospitalizations, surgical, or diagnostic procedures, the illness leading to the surgical or diagnostic procedure should be recorded as the SAE, not the procedure itself. The procedure should be captured in the narrative as part of the action taken in response to the illness.

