11.9.2. Adverse Events

All AEs will be coded using the Medical Dictionary for Regulatory Activities.

For each treatment group, the proportion of subjects with treatment-emergent adverse events (TEAEs) will be summarized overall, by severity, and by relationship to study drug. SAEs will also be summarized by treatment group. A TEAE is defined as:

- An AE that occurs after initiation of study drug that was not present at the time of treatment start.
- An AE that increases in severity after the initiation of study drug, if the event was present at the time of treatment start.

Any AE occurring before the first dose of study drug will be summarized separately.

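### SAP 11.1 classifies AEs and assigns them to study periods by onset date alone, so an existing AE that worsens can be missed as a TEAE or shown in the wrong period

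*SAP*

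**What the plan says.** Protocol 11.9.2 gives two ways for an AE to be treatment emergent. The first is a new event: "An AE that occurs after initiation of study drug that was not present at the time of treatment start". The second is worsening: "An AE that increases in severity after the initiation of study drug, if the event was present at the time of treatment start".

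SAP 11.1 has one: "Treatment emergent adverse events (TEAEs) are defined as any AEs with onset date during or after the first study treatment dose". It then splits TEAEs between the double-blind (DB) period and the OLE on the same basis: "if the AE onset date is before the date of first dose in OLE, the AE will be assigned to the DB Treatment Period". For doubtful cases it adds: "In the case where it is not possible to define an AE as treatment emergent or not, the AE will be classified as treatment emergent".

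On recording, Protocol 10.5.8.2.2 starts AE collection at consent. Protocol 10.5.8.1.5 has the investigator grade each AE at onset and adds: "When recording the outcome of the AE, the maximum severity of the AE experienced will also be recorded". The fields that 10.5.8.2.2 lists for the AE page include onset and resolution dates and severity, but no date on which a grade changed.

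SAP Table 4 lists four changes from the protocol: the OLE baseline, the FAS, the Per Protocol Set and the new OLE FAS. The TEAE definition is not among them.

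**The concern.** Safety is part of the primary objective, and the TEAE tables are its main summary. The SAP narrows the protocol's definition without saying so. An AE first noted in Screening that worsens on treatment is a TEAE under the protocol and not under the SAP.

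The period rule raises a related but separate problem. Every placebo subject who continues into the OLE starts etrasimod at Week 24, and Cohort 2 etrasimod subjects, like most in Cohort 1, go on to 3 mg. If an AE starts in the DB period and worsens after the first OLE dose, the SAP leaves the whole event in the DB period. The OLE TEAE tables then omit it, and the DB maximum-severity table can show a grade that was reached on OLE treatment.

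**Working it through.** The plan states no figure on this point, so there is none to reproduce. The check sets the texts side by side and then classifies typical AE courses.

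**Is the missing limb restored elsewhere in the SAP?** No. Appendix 2 imputes missing dates and says nothing on severity. The fallback covers AEs that cannot be classified; an AE with a known pre-dose onset can be classified, as not treatment emergent.

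**Classification, assuming one record per AE that keeps its original onset date:**

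| Course of the AE | Result under SAP 11.1 | Comment |
|---|---|---|
| Starts in Screening, worsens in the DB period, any arm | Not a TEAE | A TEAE under Protocol 11.9.2 |
| Starts in Screening, DB placebo subject, worsens on OLE etrasimod | Not a TEAE in either period | A TEAE under Protocol 11.9.2 |
| Starts on DB placebo, worsens on OLE etrasimod | DB TEAE under Placebo; not in the OLE TEAE tables | Rightly a placebo TEAE, but the maximum grade may be the OLE grade |
| Starts on DB etrasimod, worsens in the DB period | DB TEAE in its own column | Correct |
| Starts on DB etrasimod, worsens in the OLE | DB TEAE in the DB etrasimod column; not in the OLE TEAE tables | The DB grade may be the OLE grade |

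The first two rows come from the dropped limb. The third and fifth come from the period rule.

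**Can OLE grades reach the DB table at the primary analysis?** Yes. SAP section 4 runs that analysis once all subjects have finished or left the DB period, and Appendix 3 includes Week 36 OLE summaries in Batch 1. OLE data for earlier entrants will therefore be in the database when Table 14.3.1.5.1 (DB maximum severity) is produced.

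**Weight of one subject, from the planned sizes in SAP 3.2:**
- Placebo: 12 + 12 = 24, so 1/24 = 4.2 points.
- Etrasimod 2 mg: 24 + 6 = 30, so 1/30 = 3.3 points.
- Etrasimod 3 mg: 24, so 1/24 = 4.2 points.
- SAP 5.7 repeats the overall AE summary by cohort. There, one of the 12 planned placebo subjects in a cohort is 1/12 = 8.3 points.

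For the period rule these are points of a severity row. For the dropped limb, one omitted subject lowers the TEAE rate of that subject's arm by the amount shown, provided the subject has no other TEAE.

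**The case against.** Several points on the other side stand.

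- **Recording convention.** The documents do not say whether a rise in grade opens a new record. If it does, the worsening has its own post-dose onset date and both problems largely disappear. A single maximum grade per AE suggests one record but does not prove it.
- **Medical history.** Protocol 10.5.8.1.1 treats worsening of a pre-existing condition as an AE in its own right. The omission therefore mainly concerns AEs first recorded between consent and first dose, a window of up to 4 weeks.
- **Other outputs.** Affected events stay in the all-AE listing and the AE row of the overall summary. All SAEs are listed. Laboratory, vital sign, ECG, pulmonary and foveal-thickness summaries use measured values, not the TEAE flag.

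A reader might also infer three stronger things that the documents do not support.

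- **That the dropped limb moves drug toxicity into the placebo column.** It does not; the period rule does that. The protocol limb is tied to the start of study drug, which includes placebo. Restoring it alone would not move a placebo-onset event, and under the unchanged period rule it would place the second row of the table in the DB Placebo column.
- **That the errors all favour etrasimod.** Omission can occur in any arm. OLE worsening also inflates the DB etrasimod severity rows, a route open to 30 + 24 = 54 planned subjects against 24 on placebo.
- **That the placebo TEAE rate rises by 4.2 points.** An event that starts on placebo is rightly a placebo TEAE; only its severity row changes.

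**Conclusion.** The point holds. The SAP's TEAE definition is narrower than the protocol's, and the change is undeclared. That much rests on the text alone.

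The consequences rest on one assumption: that a worsening AE keeps its original onset date. If so, AEs that start before first dose and worsen on treatment are missing from the TEAE tables, whatever the arm. Under the separate period rule, DB-onset AEs that worsen in the OLE are missing from the OLE TEAE tables and can appear in the DB severity table at a grade reached later. For a DB placebo subject, that puts a grade reached on etrasimod in a Placebo severity row, at 4.2 points of that row per subject with 24 planned. For DB etrasimod subjects it inflates their own severity rows. OLE TEAE counts can only be understated by this rule. For the DB comparison, the net direction and the number of events are unknown.

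**What to change.** 1. In SAP 11.1, restore the protocol's second limb, so that an AE present at first dose whose grade rises afterwards is a TEAE. If the narrower definition is intended, declare and justify it in Table 4 instead.
2. Separately, add a worsening rule at the first OLE dose. An AE that worsens after that dose counts as an OLE TEAE at its worst OLE grade, and in the DB period only at its worst grade before OLE dosing. This should go in together with item 1, since item 1 alone would not correct the period.
3. State the eCRF convention for a change of grade.
4. Because no date of grade change is listed for collection, item 2 cannot be derived from the recorded fields alone. Query AEs ongoing at Day 1 or at the first OLE dose whose maximum grade exceeds the onset grade. SAP 7.2 already plans data reviews before the primary and final locks, for protocol deviations; the query list can be added to both. The second is needed because OLE worsening can occur after the primary lock.
5. Where the timing stays unknown, apply the SAP's existing fallback and classify the AE as treatment emergent.

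The cost is SAP wording, one derivation and a short list of site queries. No change to the design or the sample size is involved.
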